Mobile Apps to Reduce Distress in Breast Cancer Survivors using an Adaptive Design

NCT04583891

Document Date: 07/17/2021

Participants and recruitment: We will recruit 313 adult women diagnosed with breast cancer (stages 1-3) in the last 5 years (see Power analysis section in c.2.iii for justification of sample size). Only participants who screen high in symptoms of depression and/or anxiety will be enrolled. We will use both online and offline advertising, for recruitment including support from the Cancer Support Community online (<https://www.cancersupportcommunity.org>)

Inclusion criteria. (1) age \geq 18 years; (2) 0-5 years post-diagnosis of Stage I, II, or III female breast cancer; (3) elevated symptoms of depression and/or anxiety as measured by the PHQ-8 (score \geq 10) or GAD-7 (score \geq 8).

Exclusion criteria. (1) receiving or scheduled to initiate individual (1 on 1) treatment for depression and/or anxiety to avoid treatment interference (note, individuals will be permitted to enroll if they are taking antidepressant medication and have not had an appointment to adjust the dosage over the past 2 weeks); (2) mental health condition deemed to interfere with study procedures or put the participant at undue risk based on self-reported history of psychosis or bipolar disorder, or active suicidal ideation that necessitates more intense care as indicated from the Columbia-Suicide Severity Rating Scale (C-SSRS); (3) do not have an app-compatible phone (i.e., iOS 10.3 or later or Android 4.0.3 or later); and (4) cannot read and speak English (apps and coaching only available in English).

Survivors may be included if they are currently receiving or have concluded any cancer treatment (i.e., surgery, chemotherapy, radiation therapy, or hormonal therapy).

Although we considered narrowing our criteria to exclude those treated with hormonal therapy or chemotherapy, given their impact on mood and their potential impact on app uptake, we sought to investigate the efficacy of IntelliCare for a broad population of breast cancer survivors to increase the generalizability of findings. We will assess treatment factors which will allow us to characterize our sample and to examine whether treatment factors are related to app usage. The process of randomization should distribute the cancer treatment factors evenly across the IntelliCare and Patient Education conditions, thereby reducing risk of confounding the impact of treatment on outcomes.

Procedure: Figure 1 depicts the flowchart of study procedures.

[figure not shown]
Screening, enrollment, and preassessment: Interested cancer survivors will see our advertisement (Step 1), and respond by either going to our website to read the study description details and/or calling a toll-free number to discuss the details with a member of the research staff. Then, if appropriate and motivated, individuals will be directed to complete a brief online interest screen (Step 2) which will be automatically stored and then reviewed by staff to determine initial eligibility (Step 3). Ineligible individuals will be informed that they do not qualify for the study. The study coordinator will speak by

phone (Steps 4 and 5) to individuals pre-eligible based on their screener results to inform them about the study, answer all study questions, ensure eligibility using the phone screen, review the consent form, and instruct participants about the online informed consent process. Online consent forms will be completed using the IRB-approved procedure for our other digital intervention studies. A detailed medical history of eligible participants will also be taken. Participants will then complete the online pre-assessment battery online (Step 6). It is estimated that the pre-assessment battery will take 45-60 minutes to complete.

Stage 1 Randomization: After completing the pre-assessment battery, participants will be randomized to 1 of 2 conditions: 1) IntelliCare apps; or 2) App-delivered Patient Education (Steps 7 and 8). Following the procedure in prior IntelliCare trials, participants will receive a brief (10 min) enrollment call to make sure they can download and use the apps. We will use an existing onboarding phone protocol from prior trials. Specifically, the protocol walks the user through downloading the apps from the Google Play or iTunes store, enter their Study ID, and allows participants to ask questions before accepting the app use permissions. These permissions must be accepted in order for the apps to work.

Stage 2 Randomization: After monitoring app use for the first week of enrollment, participants who received the IntelliCare apps and are low-engagers of the intervention will be randomly assigned to receive added coaching or no change (Steps 9 and 10). Breast cancer survivors receiving the app-delivered Patient Education (i.e., control condition) will not be re-randomized.

Post-assessment and follow-up assessments: At the start of week nine, regardless of intervention progress or experimental group, participants will be instructed to complete the online post-assessment battery (Step 11). The post-assessment is similar to the pre-assessment battery but also includes the intervention evaluation measures, as used in our previous digital intervention studies, which provide, in part, insight into the utility, preference, and perceived efficacy of the intervention. After completing the post-

assessment battery, individuals will have continued access to their assigned program. Those that received added coaching will no longer receive coaching after the start of week nine, but will continue to have access to the apps. This same assessment battery will be completed again at 6 month (Step 12) and 12 month (Step 13) follow-ups. Participants will receive \$50 for completing the post, another \$50 for completing the 6-month follow-up, and \$100 for completing the 12-month follow up (total = \$200 as online gift certificates).

We will also conduct semi-structured interviews at the start of week nine with participants randomized to receive IntelliCare. This will enable us to identify the key themes, if any, to guide potential tailoring of the IntelliCare apps for a future study that will compare the tailored apps against the standard (i.e., untailored) apps. Individual interviews will include questions on how the apps meet their needs as a breast cancer survivor and specific changes to the apps that would make them more applicable. Potential themes that may be expressed by survivors may include using specific breast cancer examples, modifications to app look and feel, language used throughout the app, or the need for a new app component like dealing with fatigue or survivorship care planning. Information gathered from the interviews will then be used to inform possible modifications of the apps for use in a future study. In addition, we will also assess participants' preferences to receiving coaching, if any, among the low-engagers who received coaching in the IntelliCare condition. Interviews will assess the appropriateness of the timing, duration, frequency, and usefulness of coaching calls, as well as ways to improve the content of coaching calls for breast cancer survivors.

Coaching. Low-engager individuals who are randomized to the added coaching condition will receive coaching in addition to the standard IntelliCare apps. Coaching will be provided throughout the 8-week intervention period to those assigned to this condition. A coaching manual was developed for the pilot study of the IntelliCare apps among breast cancer survivors, and was modelled on a manual developed and refined by co-Investigator [name] and consultant [name]. The manual is based on the Efficiency Model of Behavioral Intervention Technology Support.

Coaching is meant to support participants' utilization of the IntelliCare apps. Coaches target potential points at which users may fail to benefit from the program. These "failure points" include issues related to the usability of the program, engagement with it, fit of the program tool to one's needs, knowledge of how to use the program, and implementation failures (e.g. one practices the skills using the program tools, but does not use them in day to day life). Once a failure point is identified, the coach provides support to the user to help address the obstacles that may be in the way of using the application. In keeping with prior studies, coaches will not be providing traditional counseling or psychotherapy. Rather, the coaching is focused on identifying and addressing barriers to application utilization. An initial 30-45 minute coaching call will focus on orienting participants to using the apps, setting expectations of the coach's role, assessing how the apps may meet participants' needs, and building rapport. This

will be done in a semi-structured interview format. Participants will also be encouraged to contact coaches at any time, using email or text, with any app-related questions. Following the initial coaching call, participants will receive a text message every week from the coach to remind them to download and try 1-2 new IntelliCare apps. We will conduct fidelity assessments based on procedures from prior IntelliCare trials. Bachelor's degree-level coaches will be trained and monitored by the PI ([name]) with the support of consultant [name], who each have a PhD in clinical psychology and over 8 years of experience in conducting psychological assessments and psychotherapy. Coaches will receive a detailed coaching manual and will attend weekly supervision meetings throughout the trial. Coaches will also be trained to use an existing researcher-facing web portal, which has been used in multiple IntelliCare trials, to track app usage as well as send and receive text messages.

Mobile Apps to Reduce Distress in Breast Cancer Survivors using an Adaptive Design

NCT04583891

Document Date: 12/2/2024

Aim1: Test the impact of the IntelliCare apps on reducing symptoms of depression and anxiety in breast cancer survivors.

We will compare the efficacy of the IntelliCare apps vs. app-delivered Patient Education in reducing symptoms of depression and anxiety from pre-intervention to post intervention and 6 and 12 month follow ups. To obtain the main effect of the IntelliCare apps on symptom reduction, it is important to account for the potential confound of added coaching that some of the low-engagers will receive. The impact of IntelliCare apps on depression and anxiety symptoms will be examined using a potential outcomes framework and marginal structural models (MSM).¹²⁴ Because all low-engagers of the IntelliCare apps will be re-randomized to receive either added coaching or no change, we are able to assign weights to assess the marginal mean for participants under the condition that nobody received added coaching, and compare it to the marginal mean for individuals that received app-delivered Patient Education. The IntelliCare condition will be estimated by using Inverse Probability of Treatment Weights.¹²⁵ Specifically, participants that received the IntelliCare apps will be assigned a weight of 2 if they were identified as low-engagers and then randomized to continue the apps with no change, and will be assigned a weight of 1 if they were not re-randomized (i.e., they were identified as high-engagers). Participants that were re-randomized to receive added coaching will be assigned a weight of 0 which negates their impact. This is done to account for the potential impact of added coaching on the efficacy of the IntelliCare apps.

After data is appropriately weighted, we will use a regression based approach for statistical hypothesis testing. We will use the mixed model repeated measures (MMRM) method for repeated measures models with weights as recommended for SMART designs. The weighted treatment and control means at baseline, post, 6m, and 12m will then be regressed as a function of treatment, time point, and treatment by time interaction. Using this model, we will be able to test for the presence of individual interaction effects. Statistical significance ($p < .05$) will imply differential change in symptoms of depression and anxiety due to the impact of the IntelliCare apps vs. app-delivered Patient Education at each time point.

Aim 2. Test the impact of added coaching on engagement with the IntelliCare apps.

The purpose of Aim 2 is to test whether coaching results in greater engagement with the IntelliCare apps. Therefore, app engagement is the outcome. We will examine three aspects of app engagement in separate analyses: app launches and number of days used. Medians, adjusted means, and interquartile ranges will be examined. MMRM with adjusted means will be used to evaluate whether added coaching led to increased app engagement with IntelliCare compared to no added coaching in weeks 2-8, for suboptimal engagers after week 1.

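### Efficiency improvement, not an error: adjusting Aim 1 for the baseline score would usually give a tighter estimate of the same contrast than the planned treatment-by-time test

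*SAP*

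**What the plan says.** SAP, Aim 1: the objective is to compare the arms "in reducing symptoms of depression and anxiety from pre-intervention to post intervention and 6 and 12 month follow ups". Weights of 2, 1 and 0 in the IntelliCare arm are meant to "assess the marginal mean for participants under the condition that nobody received added coaching". For the model, "The weighted treatment and control means at baseline, post, 6m, and 12m will then be regressed as a function of treatment, time point", with treatment-by-time as the remaining term. The SAP adds: "Using this model, we will be able to test for the presence of individual interaction effects". A p-value below .05 is read as differential change at that time point. Aim 1 is given no baseline covariate and no common baseline mean. The phrase about adjusted means belongs to Aim 2, where the outcome is app engagement.

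Protocol, Participants and recruitment: "Only participants who screen high in symptoms of depression and/or anxiety will be enrolled". The inclusion criterion is "elevated symptoms of depression and/or anxiety as measured by the PHQ-8" at 10 or more, or GAD-7 at 8 or more.

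Protocol, Procedure: the pre-assessment battery is Step 6, and "After completing the pre-assessment battery, participants will be randomized to 1 of 2 conditions".

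**The concern.** Because randomization follows the pre-assessment, any baseline difference D between the arms is chance. The SAP weights keep this true if re-randomization is 1:1, as a weight of 2 implies: a low-engager has weight 2 or 0 with equal probability, so the average weight is 1 whatever her baseline score.

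The planned contrast subtracts D in full. Only slope × D is expected to persist to follow-up, where slope is the regression of follow-up on baseline. The planned estimate is thus moved by −(1 − slope)·D, which is noise. A baseline-adjusted contrast removes only slope × D. Since D has expectation zero, it targets the same difference in mean change that Aim 1 describes.

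What is at stake is the width of the intervals for depression and anxiety at post, 6 months and 12 months.

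**Working it through.** **Inputs.** From the documents: N = 313; baseline measured before Stage 1 randomization; entry at PHQ-8 ≥ 10 or GAD-7 ≥ 8; weights 2/1/0. Not in the documents, so assumed: k, rho, the low-engager share and the outcome scales (the SAP does not name them). The supplied text contains no power section, so 313 cannot be reproduced; that is not evidence of an error.

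**Step 1. General formula** (common covariance, complete data). Set follow-up SD to 1 and baseline SD to k.
- Planned (change): 1 + k² − 2·rho·k
- Adjusted: 1 − rho²
- Planned minus adjusted: (k − rho)², never negative
- Extra participants for equal precision: (k − rho)²/(1 − rho²)

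Here k and rho are the values among enrolled women.

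| k | rho 0.3 | rho 0.5 | rho 0.7 |
|---|---|---|---|
| 0.7 | 0.16/0.91 = 18% | 0.04/0.75 = 5% | 0% |
| 0.85 | 0.3025/0.91 = 33% | 0.1225/0.75 = 16% | 0.0225/0.51 = 4% |
| 1.0 | 0.49/0.91 = 54% | 0.25/0.75 = 33% | 0.09/0.51 = 18% |
| 1.2 | 0.81/0.91 = 89% | 0.49/0.75 = 65% | 0.25/0.51 = 49% |

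**Step 2. Effect of the entry cut-offs.** If outcomes are on the entry scales or close relatives, selection narrows the baseline. Assume normal scores, a correlation of 0.6 to 0.75 between the two scales, equal cut-offs 0 to 1 SD above the mean, entry on either scale, and follow-up depending on selection only through its own baseline. From 4,000,000 draws, the share of baseline variance left is v = 0.42 to 0.64. Let s be follow-up SD over baseline SD, and rho the correlation, both before selection. Selection leaves the slope at rho·s, so

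excess = v·(1 − rho·s)² / [s²·(1 − rho²)].

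| s | rho 0.3 | rho 0.5 | rho 0.7 |
|---|---|---|---|
| 0.8 | 0.992v = 42–63% | 0.750v = 32–48% | 0.593v = 25–38% |
| 1.0 | 0.538v = 23–34% | 0.333v = 14–21% | 0.176v = 7–11% |
| 1.2 | 0.313v = 13–20% | 0.148v = 6–9% | 0.035v = 1–2% |
| 1.4 | 0.189v = 8–12% | 0.061v = 3–4% | about 0% |

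At s = 1, intervals are wider by the square root of these: 11–16%, 7–10% and 4–5%.

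**Step 3. Does it survive the weights?** In a simulation with N = 313, weights 0/1/2, robust standard errors and engagement correlated 0.3 with baseline (4,000 runs per setting, k = 1, true difference −0.30), both estimators averaged about −0.30. Adjusted/planned variance was 0.65–0.66, 0.75–0.77 and 0.84–0.86 at rho 0.3, 0.5 and 0.7, against (1 + rho)/2 = 0.65, 0.75 and 0.85. At k = 0.7 it was 0.96 (rho 0.5) and 1.00 (rho 0.7).

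**Step 4. Covariance that differs by engagement.** Let q be the low-engager share. The expected squared weight is 1 for high-engagers and 2 for low-engagers. With equal group means, variance is proportional to (1 − q)·g(high) + 2q·g(low) + g(control), where g(r) = 1 + B²k² − 2Brk. The planned contrast has B = 1; the adjusted has B = [(1 − q)·r_high + q·r_low + r_control]/(2k).

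Example: k = 0.8, q = 0.5, correlations 0.4 (high), 0.7 (low), 0.5 (control). B = 1.05/1.6 = 0.656. Planned: 0.5·1.00 + 0.52 + 0.84 = 1.860. Adjusted: 0.5·0.856 + 0.541 + 0.751 = 1.719. Excess 8%.

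Over 7,680 combinations (k 0.6 to 1.0; each correlation 0.2 to 0.9; q 0.2, 0.5, 0.8) the adjusted contrast was less precise in 424 (5.5%), by at most 2.2%.

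**The case against.** The strongest reply is that nothing is wrong. Aim 1 asks about change from pre-intervention, treatment-by-time answers exactly that, and the choice lies between two acceptable analyses. This stands as far as it goes: the planned test is valid, and a reader who infers bias or an invalid p-value goes beyond the documents. It does not answer an efficiency point, because the adjusted analysis addresses the same contrast.

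Second, the size is not known. This also stands. Step 2 shows how far the s = 1 row depends on equal SDs before selection: the excess nearly vanishes at s = 1.4 with rho 0.7 and reaches 63% at s = 0.8 with rho 0.3. Nor is k = 1 a ceiling. If scores fall toward the floor after treatment, follow-up spread can be smaller than baseline spread, and the k = 1.2 row applies.

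Third, the SAP follows a weighted repeated-measures method recommended for SMART designs, and its source might specify covariates. This is weak: the SAP lists its own terms and baseline adjustment is not among them.

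Fourth, the SAP is dated 12/2/2024, against 07/17/2021 for the protocol, and does not say whether outcomes by arm had been seen. A late change of the main contrast has a credibility cost, so the change cannot be called free without condition.

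A reader might also infer that 313 is too few or that a conclusion would change. The supplied text gives no effect size, SD, power or dropout, so neither can be said.

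**Conclusion.** The point holds as an efficiency improvement. The model leaves baseline unconstrained although randomization makes the expected baseline means equal. With a common covariance and complete data, adjustment is never less precise in large samples and ties only when k equals rho. If covariance differs by engagement group, the gain is usual but not guaranteed; the worst loss in the grid examined was about 2%.

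The algebra is firm. The size for this trial is not: about none to substantial, with 7–34% as one illustration (either-scale selection, equal SDs before selection, pre-selection rho 0.3 to 0.7). All of this assumes 1:1 re-randomization.

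**What to change.** Preferred: keep the SAP weights. Take baseline out of the outcome vector, enter each outcome's own baseline score with a baseline-by-time term, and test treatment at post, 6 months and 12 months with a robust (sandwich) variance.

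Alternative: keep baseline as an outcome but constrain its mean to be common to both arms, only with a correlated within-person covariance such as unstructured. Under working independence this becomes a follow-up-only comparison, with variance (rho²v + 1 − rho²)/((1 − rho)²v + 1 − rho²) times that of the planned contrast. At s = 1 and v = 0.42 to 0.64 this is 0.79–0.85, 1.00 and 1.31–1.45 at rho 0.3, 0.5 and 0.7, so it is worse than the plan above 0.5.

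Cost: a few sentences on mean model, covariance and variance estimator; no new data or participants. If outcomes by arm are still unseen, that is all. If they have been seen, date the change, keep the planned interaction test as the stated primary, and report the adjusted analysis alongside it.

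### Does the SAP's sentence about regressing weighted means leave the Aim 1 test with no degrees of freedom, or change how dropout is handled?

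*SAP*

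**What the plan says.** The SAP's Aim 1 text sets out the analysis in three steps.

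1. **Weights.** IntelliCare participants get weight 2 (low-engager, no change), 1 (not re-randomized) or 0 (low-engager, coached). The purpose is given as "we are able to assign weights to assess the marginal mean for participants under the condition that nobody received added coaching".
2. **Method.** "We will use the mixed model repeated measures (MMRM) method for repeated measures models with weights as recommended for SMART designs".
3. **Model terms.** "The weighted treatment and control means at baseline, post, 6m, and 12m will then be regressed", continuing "as a function of treatment, time point, and treatment by time interaction". The SAP then refers back to this as one model, used to test individual interaction effects. Significance is read as differential change "due to the impact of the IntelliCare apps vs. app-delivered Patient Education at each time point".

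The supplied text does not state the covariance structure, the standard-error method, the coding of time or a missing-data assumption. The Protocol's section on post-assessment and follow-up asks everyone for the post-assessment battery "regardless of intervention progress or experimental group" and repeats the battery at 6 and 12 months.

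**The concern.** Two adjacent sentences seem to name different response variables. An MMRM takes each participant's score at each visit. The next sentence makes the weighted arm means the thing regressed.

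Two consequences would follow if the second sentence governed:

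- **No test.** A model with treatment, three visit terms and three interactions fits eight means exactly and leaves nothing to estimate error.
- **Different handling of dropout.** Suppose the regression were run on participant rows with independent errors. It would return the observed weighted mean at each visit, so a woman lost after the post-assessment would add nothing to the 6- and 12-month contrasts. An MMRM with a modelled covariance still uses her earlier scores. If dropout followed the last score more strongly in one arm, the first approach would bias the Aim 1 contrast and the second would not.

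The 2/1/0 weights do not settle this, because they deal with coaching assignment and not with non-response.

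**Working it through.** **Degrees of freedom, literal reading.** Inputs: 2 arms and 4 visits, from the SAP. Categorical time is implied by a contrast at each time point but is not stated.

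- Means: 2 × 4 = 8.
- Coefficients: 1 intercept + 1 treatment + 3 time + 3 interaction = 8.
- Residual df: 8 − 8 = 0. The design matrix has rank 8.
- With linear time instead: 4 coefficients and 8 − 4 = 4 residual df. That coding does not fit a test at each visit.

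**Degrees of freedom, named method.** The mean structure is the same 8 parameters, but the response is the participant's score.

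- Maximum number of scores: 313 × 4 = 1,252.
- Coached participants have weight 0. Assuming 157 in IntelliCare, 50% low-engagers and even re-randomization, they number about 157 × 0.5 × 0.5 ≈ 39. That leaves 313 − 39 = 274 participants and 274 × 4 = 1,096 scores.
- Either count is ample for 8 means and a 4 × 4 covariance matrix.

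A saturated set of means is therefore normal for an MMRM with treatment, visit and their interaction. The count of 8 against 8 does not by itself show a fault.

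**Dropout.** The documents give no SD, correlation, dropout rate or allocation ratio, so everything below is assumed.

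*First set.* 157 per arm, SD 5, correlation 0.6, 50% low-engagers, 27–33% missing at 12 months, true 12-month difference in change −2.0, 400 trials per row.

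| Dropout depends on the prior score | Observed visit means | Weighted MMRM |
|---|---|---|
| Not at all | −1.97 | −1.97 |
| Equally in both arms | −1.98 | −1.98 |
| In IntelliCare only | −2.95 | −2.01 |
| In opposite directions | −3.93 | −2.01 |

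The slope was 0.2 in log-odds per point, which is 0.2 × 5 = 1.0 per SD. The IntelliCare-only bias of visit means is −2.95 − (−2.0) = −0.95.

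*Second set.* SD 5, correlation 0.55, response about 86/79/73% at post/6m/12m, dependence in IntelliCare only. Size of bias in points:

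| Slope per SD | Visit means, post/6m/12m | MMRM |
|---|---|---|
| 0.25 | 0.09/0.17/0.22 | within 0.02 |
| 0.5 | 0.20/0.32/0.43 | within 0.02 |
| 1.0 | 0.45/0.69/0.90 | within 0.02 |

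Two-sided error for visit means was 6/8/9% at 0.5 per SD and 10/16/22% at 1.0; for MMRM it was 5%. With equal dependence in both arms at 1.0 per SD, visit-mean bias was about 0 with no effect and 0.00/0.09/0.13 with a 2-point effect.

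The two sets agree at the steepest slope (0.95 and 0.90 at 12 months). Both show that the approaches part only when score-related dropout differs by arm, apart from the small differences in the equal-dependence case with an effect.

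**Which analysis the figures describe.** The visit-mean columns come from participant rows fitted with independent errors. The literal regression of eight means cannot produce them, because it has no error variance. The named MMRM does not produce them either, because it models the covariance. They belong to a third analysis that the SAP does not set out.

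**The case for a change.** The strongest reply is that the MMRM label alone does not protect against dropout. The protection comes from the covariance model. A weighted repeated-measures fit with working independence gives back the observed visit means, and the SAP names no covariance structure to exclude it. Two analysts could in principle reach different Aim 1 estimates from the same text. The remedy would also be cheap: a reworded sentence that keeps the sponsor's method, weights and contrasts.

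Part of this stands. The sentence is loose, and the response level, time coding, covariance, standard errors and missing-data assumption are not written down in the text supplied.

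It falls short for three reasons. An independent-errors fit conflicts with the method the SAP names, since modelling within-participant correlation is what distinguishes an MMRM. The literal reading is not one an analyst could mistakenly carry out: it yields no residual-based p-value, and the obvious repair, standard errors taken from participant data, leads back to the participant level. And no passage suggests that score-related dropout will differ by arm, so the size of any harm cannot be fixed from the documents.

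**Conclusion.** No change to the plan is needed. The weights attach to people, the method is named in the sentence just before, and the interaction tests are drawn from that one model. The phrase about means is best read as describing what the weighted MMRM estimates: marginal means by arm and visit. Likelihood-based MMRM conventionally assumes that non-response depends on observed data, and a contrast at each visit points to categorical time, so the unstated items have ordinary defaults.

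The 0 residual df is correct only for the literal reading with categorical time, and it rules out only a residual-based test. Bias of 0.09 to 0.90 points, across post to 12 months and slopes of 0.25 to 1.0 per SD, is correct only for an independent-errors fit under assumed one-arm dropout. The method actually named stayed within 0.02 points in those scenarios. Writing out the details would record the planned analysis more fully but would not alter it. The conclusion rests on the analyst fitting the named MMRM with a modelled covariance to participants' own scores. The supplied text may also be an extract, since the Protocol refers to a power section that is not included.

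### Does announcing three engagement outcomes but naming two leave the SAP's Aim 2 short of a planned analysis?

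*SAP*

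**What the plan says.** The Aim 2 section of the SAP sets a single question: "The purpose of Aim 2 is to test whether coaching results in greater engagement with the IntelliCare apps". It makes engagement the outcome and then gives the list: "We will examine three aspects of app engagement in separate analyses: app launches and number of days used". The next sentence turns to presentation: "Medians, adjusted means, and interquartile ranges will be examined". The section closes with the analysis itself, a mixed model for repeated measures with adjusted means. The model looks for "increased app engagement with IntelliCare compared to no added coaching in weeks 2-8" among participants whose use was low after the first week.

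The protocol has no list of engagement outcomes. Under Stage 2 Randomization it says that app use is monitored during the first week. Under Coaching it says that coaches follow usage through a web portal. Neither place names a metric.

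**The concern.** A count that disagrees with its list deserves a second look when the list is the set of outcomes. If the count is right, one planned analysis has no name and no definition. It would be absent from the report, and no reader could notice. If the list is right, the count is a typing error and nothing is lost. The text does not say which.

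Two other features add to the unease. The SAP carries a much later date than the protocol, and the documents do not say whether engagement data had been seen by then. Also, launches and days of use do not exhaust what engagement could mean. The Protocol's Coaching section says "participants will receive a text message every week from the coach to remind them to download and try 1-2 new IntelliCare apps", and neither named metric counts how many different apps a participant tried. A third metric would therefore not have to repeat the other two.

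**Working it through.** **Count.** Announced in the SAP, Aim 2: 3. Named after the colon: launches (1), days of use (2). Difference: 3 − 2 = 1. The stated count cannot be reproduced from the list.

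**Could the third item be elsewhere?** The sentence after the list does contain three things, but they are a median, an adjusted mean and an interquartile range. These are ways of summarising an outcome and cannot be outcomes analysed separately. The protocol names no engagement metric at all. The list sentence is grammatically complete and shows no redaction mark, so nothing suggests a removed item, although loss when the PDF was read cannot be fully excluded.

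**Can the named analyses be run?** Each needs five things, and each has them:

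- outcome: launches, or days of use;
- model: repeated-measures mixed model with adjusted means;
- comparison: added coaching against none, assigned at random in Stage 2;
- window: weeks 2 to 8;
- population: low engagers after week 1 in the IntelliCare arm.

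The outcomes are analysed separately, and the SAP states no division of a significance level among them. The number of outcomes therefore enters neither model and neither test. Going from three to two, or from two to three, leaves the results for launches and for days unchanged.

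**What does the count change, if anything?** The SAP states the .05 level for Aim 1 only. Assume, for illustration, that each Aim 2 outcome is also tested at .05 and that the tests are independent. The chance of at least one false positive is 1 − 0.95² = 0.0975 with two and 1 − 0.95³ = 0.1426 with three. Outcomes drawn from the same usage log are likely to be positively correlated, which would bring both figures down.

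A second illustration is the chance that the outcomes disagree, some significant and some not. Assume equal power and equally correlated test statistics, and let p be the chance of significance given the shared component:

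- two outcomes: E[2p(1 − p)];
- three outcomes: 1 − E[p³] − E[(1 − p)³] = E[3p(1 − p)].

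The second is always 3/2 = 1.5 times the first. At an assumed 80% power the figures are 10.0% and 15.0% with correlation 0.9, and 22.6% and 33.9% with correlation 0.5. The power and correlation have no source in the documents. The fixed ratio shows that the comparison reflects the number of tests and says nothing about whether an outcome was lost.

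**Dates.** Protocol: "Document Date: 07/17/2021". SAP: "Document Date: 12/2/2024". From 17 July 2021 to 17 July 2024 is 3 × 365 + 1 = 1,096 days. From there to 2 December 2024 is 138 days. The total is 1,234 days, about 40.5 months. To show that a list had been altered in that time one would need two lists, and the protocol has none.

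**The case for a change.** The strongest case for action is that Aim 2 is one of only two aims in the SAP, engagement is its sole outcome, and the error sits in the list of outcomes itself. Only the sponsor knows whether two or three was meant. A silent correction to two would leave open whether an outcome was dropped after usage data were available. A dated note costs almost nothing.

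Part of this stands. The mismatch is real, no other text resolves it, and a short statement from the sponsor would be welcome.

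The rest does not carry a change to the plan. It would be wrong to say that one of three analyses is undefined, because that takes the count as correct when the count is what is in doubt. The coaches' weekly reminder is a coaching procedure. It shows that a different metric is conceivable, but it is no evidence that one was planned. The document date does not tell us when this sentence was written, and the section is in the future tense. The supplied text also appears to be extracted from something longer: the protocol refers to a power analysis in section c.2.iii that is not included, and the SAP carries reference numbers 124 and 125 without a reference list. The fuller source may settle the count.

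How to read mixed results, whether to report one overall effect across weeks 2 to 8, and whether to adjust for multiple outcomes are separate matters. They would arise with either count, and the SAP already commits to separate analyses.

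**Conclusion.** This is most likely a clerical slip. The discrepancy is one item, and it affects neither of the two analyses that the SAP defines, nor Aim 1. An analyst following the text would fit one model for launches and one for days of use, and would obtain sound randomised comparisons of coaching with no added coaching.

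The conclusion assumes that the two named outcomes are the complete list. That is the simpler reading, since both are named and neither document mentions another, but it is not proved. If a third outcome had been specified, Aim 2 reporting would be incomplete by one analysis, while the two named results would remain valid. Because the documents do not establish which case applies, they support no specific amendment: there is no identified outcome to restore and no method to alter. Making the count agree with the list is a matter of wording for the sponsor, not a change to the analysis plan.
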